B7: Other Relevant History, Including Preexisting Medical Conditions

Knowledge of other risk factors can help in the evaluation of a reported adverse event. If available, provide information on:

- **Other known conditions in the patient, e.g.,**
 - Hypertension (high blood pressure)
 - Diabetes mellitus
 - Liver or kidney problems
- **Significant history**
 - Race
 - Allergies
 - Pregnancy history
 - Smoking and alcohol use, drug abuse
 - Setting

SECTION C: PRODUCT AVAILABILITY

Product available for evaluation? (Do not send the product to FDA.)

To evaluate a reported problem with a medical product, it is often critical to be able to examine the product. Please indicate whether the product is available for evaluation. Also indicate if the product was returned to the manufacturer and, if so, the date of the return.

SECTION D: SUSPECT PRODUCT(S)

For adverse event reporting:

A suspect product is one that you suspect is associated with the adverse event. In **Section F** enter other concomitant medical products (drugs, biologics including human cells, tissues, and cellular and tissue-based products (HCT/Ps), medical devices, etc.) that the patient was using at the time of the event but which you do not think were involved in the event.

Up to two (2) suspect products may be reported on one form (#1=first suspect product, #2=second suspect product). Attach an additional form if there were more than two suspect products associated with the reported adverse event.

For product quality problem reporting:

A suspect product is the product that is the subject of the report. A separate form should be submitted for each individual product problem report.

Identification of the labeler/distributor and pharmaceutical manufacturer and labeled strength of the product is important for prescription or non-prescription products.

This section may also be used to report on special nutritional products (e.g., dietary supplements, infant formula or medical foods), cosmetics, human cells, tissues, or cellular and tissue-based products (HCT/Ps) or other products regulated by FDA.

If reporting on a special nutritional or drug product quality problem, please attach labeling/packaging if available.

If reporting on a special nutritional product only, please provide directions for use as listed on the product labeling.

D1: Name, Strength, Manufacturer

Use the trade/brand name. If the trade/brand name is not known or if there is no trade/brand name, use the generic product name and the name of the manufacturer or labeler. These names are usually found on the product packaging or labeling. Strength is the amount in each tablet or capsule, the concentration of an injectable, etc. (such as "10mg", "100 units/cc", etc.).

For human cells, tissues, and cellular and tissue-based products (HCT/Ps), please provide the common name of the HCT/P. You can also indicate if the HCT/P has a proprietary or trade name. Examples: Achilles tendon, Iliac crest bone or Islet cells.

D2: Dose or Amount, Frequency, Route

Describe how the product was used by the patient (e.g., 500 mg QID orally or 10 mg every other day IV). For reports involving overdoses, the amount of product used in the overdose should be listed, not the prescribed amount. (See **APPENDIX** for list of **Routes of Administration** on the next page.)

D3: Dates of Use

Provide the date administration was started (or best estimate) and the date stopped (or best estimate). If no dates are known, an estimated duration is acceptable (e.g., 2 years) or if therapy was less than one day, then duration is appropriate (e.g., 1 dose or 1 hour for an IV).

For human cells, tissues, and cellular and tissue-based products, provide the date of transplant and if applicable, the date of explanation.

D4: Diagnosis or Reason for Use (Indication)

Provide the reason or indication for which the product was prescribed or used in this particular patient.

D5: Event Abated After Use Stopped or Dose Reduced

If available, this information is particularly useful in the evaluation of a suspected adverse event. In addition to checking the appropriate box, please provide supporting lab tests and dates, if available, in block **B6**.

D6: Lot #

If known, include the lot number(s) with all product quality problem reports, or any adverse event report with a biologic, or medication.

D7: Expiration Date

Please include if available.

(continued on next page)

SECTION D: SUSPECT PRODUCT(S) (continued)

D8: Event Reappeared After Reintroduction

This information is particularly useful in the evaluation of a suspected adverse event. In addition to checking the appropriate box, please provide a description of what happened when the drug was stopped and then restarted in block **B5**, and any supporting lab tests and dates in block **B6**.

D9: NDC # or Unique ID

The national drug code (NDC #) is requested only when reporting a drug product problem. Zeros and dashes should be included as they appear on the label. NDC # can be found on the original product label and/or packaging, but is usually not found on dispensed pharmacy prescriptions.

If the product has a unique or distinct identification code, please provide this here. This is applicable to human cells, tissues, and cellular and tissue-based products (HCT/PS).

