529	Nervous system disorders	Central nervous system necrosis	Severe symptoms; medical intervention indicated	Accepted treatments for malignant glioma (for example radiation therapy) can produce CNS necrosis that requires medical intervention such as corticosteroid administration
531	Nervous system disorders	Cognitive disturbance	Severe cognitive disability; significant impairment of work/school/life performance	Both malignant glioma and its accepted therapies (for example radiation therapy) can produce impairment of work/school/life performance
532	Nervous system disorders	Concentration impairment	Severe impairment in attention or decreased level of concentration; limiting self care ADL	Both malignant glioma and its accepted therapies (for example radiation therapy) can produce impairment in attention or decreased level of concentration that affects self care ADL
536	Nervous system disorders	Dysesthesia	Severe sensory alteration; limiting self care ADL	Malignant glioma can produce alterations in sensory function limiting self care ADL
545	Nervous system disorders	Headache	Severe pain; limiting self care ADL	Malignant glioma can result in intracranial pressure resulting in severe headaches
567	Nervous system disorders	Pyramidal tract syndrome	Severe symptoms; limiting self care ADL	Malignant glioma can produce dysfunction of the pyramidal tract
571	Nervous system disorders	Seizure	Multiple seizures despite medical intervention	Malignant glioma can produce multiple seizures despite medical intervention
575	Nervous system disorders	Stroke	Severe neurologic deficit	Malignant glioma can produce stroke through its associated hypercoagulative state. Also, treatment for malignant glioma (for example bevacizumab, radiation) can result in stroke

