10.1 Adverse Event Reporting (AE; formerly known as Adverse Drug Reaction)

10.1.1 Adverse Event

An adverse event (AE) is defined as any untoward medical occurrence associated with the use of a drug in humans, whether or not considered drug related. An AE can be any unfavorable and unintended sign (e.g., abnormal laboratory finding), symptom, or disease temporally associated with the use of a drug, without any judgment about causality. An AE can arise from any use of the drug and from any route of administration, formulation, or dose, including an overdose.

An illness or condition present at study entry is considered a pre-existing condition and will not be considered an AE unless the pre-existing condition worsens during the course of the study. This change may be considered an AE. An AE that occurs after signing informed consent but prior to the administration of study drug will be considered not related to study treatment.

AE's that have a grade increase to 4 or 5 will be considered an SAE and reported as required.

All AE's, irrespective of relationship to study drug, which occur or worsen after signing of consent form until 30 days after administration of study drug, must be reported and documented on the AE Case

Report Form (CRF). All medications given for an AE will be reported on the Concomitant Medication CRF.

Hospitalizations that are expected due to the disease and those that are unrelated to the study drug or disease will be reported as AE’s unless it meets the requirements for a serious adverse event (SAE) which can be found in Section 10.1.2. Hospitalizations due to merely diagnostic reasons, examinations as a matter of routine or planned surgery and due to social indication do not represent a hospitalization in the sense of the term “serious”.

An AE is considered unexpected if it is not listed in **Section 5.1**.

10.1.2 Serious Adverse Event Expedited Reporting Guidelines – Phase 1 studies with investigational agents:

A serious adverse event (SAE) is defined as:

- Unexpected AE
 - For grade 1, no expedited reporting required
 - For grade 2, the investigator will be unbiased in assessing the relationship of the event and test article and discuss the possible relatedness to treatment with the Medical Monitor. If found to be possibly, probably or definitely related to study drug, an expedited report will be submitted within 7 working days.

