 - For grade 3, the investigator will be unbiased in assessing the relationship of the event and test article and discuss the possible relatedness to treatment with the Medical Monitor. If found to be possibly, probably or definitely related to study drug, an expedited report will be submitted by phone within 24 hours with expedited report to follow within 7 working days.
 - For grade 4-5, regardless of relationship to study drug, a report will be submitted by phone within 24 hours with expedited report to follow within 7 working days.
- AE whose grade has increased to grade 3 or 4
- Adverse Event and IND safety reports will be filed in a timely manner with institutional authorities (IRB, IBC) as well as with the FDA and NIH/ORDA.
- All serious adverse events (Grade 3 or 4 toxicities) will be reported by fax, e-mail or phone within 24 hours and a written expedited report filed within seven days. Additionally, unexpected Grade 2 or Grade 3 toxicities will require a written expedited report within seven

days and Grade 3 unexpected adverse events will also require a fax, email, or phone call to the UAB IRB, the Neuro-Oncology CTMC, CCC PRC, FDA, and OBA within 24 hours.

- For events that are related, unexpected and serious, reporting will be reported to the FDA within 7 days of knowledge of the event.
- A list of agent-specific expected adverse events can be found in Appendix A.
- Any adverse event requiring an expedited report will also be reported immediately to the Medical Monitor and the investigator’s Institutional Review Board (IRB).

UNEXPECTED EVENT		EXPECTED EVENT	
GRADES 2 – 3 Attribution of Possible, Probable or Definite	GRADES 4 and 5 Regardless of Attribution	GRADES 1 - 3	GRADES 4 and 5 Regardless of Attribution
Grade 2 - Expedited report within 7 working days. Grade 3 - Report by phone to IDB within 24 hrs. Expedited report to follow within 7 working days.	Report by phone to IDB within 24 hrs. Expedited	Adverse Event Expedited	Report by phone to IDB within 24 hrs. Expedited report to follow within 7 working days.

(Grade 1 – Adverse Event Expedited Reporting NOT required.)	report to follow within 7 working days. This includes deaths within 30 days of the last dose of treatment with an investigational agent.	Reporting NOT required.	This includes deaths within 30 days of the last dose of treatment with an investigational agent.
---	---	-------------------------	--

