- Suspected counterfeit product
• Suspected contamination
• Questionable stability
• Defective components
• Poor packaging or labeling
• Therapeutic failures (product didn't work)

Report SERIOUS adverse events. An event is serious when the patient outcome is:

- Death
• Life-threatening
• Hospitalization - initial or prolonged
• Disability or permanent damage
• Congenital anomaly/birth defect
• Required intervention to prevent permanent impairment or damage (devices)
• Other serious (important medical events)

Report even if:

- You're not certain the product caused the event
• You don't have all the details

How to report:

- Just fill in the sections that apply to your report
• Use section D for all products except medical devices
• Attach additional pages if needed
• Use a separate form for each patient
• Report either to FDA or the manufacturer (or both)

Other methods of reporting:

- [name] - To FAX report
• [name] - To report by phone
• www.fda.gov/medwatch/report.htm - To report online

If your report involves a serious adverse event with a device and it occurred in a facility outside a doctor's office, that facility may be legally required to report to FDA and/or the manufacturer. Please notify the person in that facility who would handle such reporting.

If your report involves a serious adverse event with a vaccine, call [name] to report.

Confidentiality: The patient's identity is held in strict confidence by FDA and protected to the fullest extent of the law. FDA will not disclose the reporter's identity in response to a request from the public, pursuant to the Freedom of Information Act. The reporter's identity, including the identity of a self-reporter, may be shared with the manufacturer unless requested otherwise.

-Fold Here-

-Fold Here-

The public reporting burden for this collection of information has been estimated to average 36 minutes per response, including the time for reviewing instructions, searching existing data sources, gathering and maintaining the data needed, and completing and reviewing the collection of information. Send comments regarding this burden estimate or any other aspect of this collection of information, including suggestions for reducing this burden to:

Department of Health and Human Services
Food and Drug Administration
Office of Chief Information Officer
[name]
[name]

Please DO NOT RETURN this form to this address.

OMB statement:

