- If the patient is less than 3 years old, use month (e.g., 24 months).
- If the patient is less than 1 month old, use days (e.g., 5 days).
- Provide the best estimate if exact age is unknown.

A3: Sex

Enter the patient's gender. If the adverse event is a congenital anomaly/birth defect, report the sex of the child.

A4: Weight

Indicate whether the weight is in pounds (lb) or kilograms (kg). Make a best estimate if exact weight is unknown.

SECTION B: ADVERSE EVENT, PRODUCT PROBLEM, PRODUCT USE ERROR

B1: Adverse Event, Product Problem, Product Use Error, or Problem with Different Manufacturer of Same Medicine.

Choose the appropriate box(es). If a product problem may have caused or contributed to the adverse event, check both boxes.

Adverse event: Any incident where the use of a medication (drug or biologic, including HCT/P), at any dose, a medical device (including *in-vitro* diagnostics) or a special nutritional product (e.g., dietary supplement, infant formula or medical food) is suspected to have resulted in an adverse outcome in a patient.

To report, it is not necessary to be certain of a cause/effect relationship between the adverse event and the use of the medical product(s) in question. Suspicion of an association is sufficient reason to report. Submission of a report does not constitute an admission that medical personnel or the product caused or contributed to the event.

Please limit your submissions to those events that are serious. An event is classified as serious when the patient outcome is:

- Death
- Life-threatening
- Hospitalization (initial or prolonged)
- Disability or Permanent Damage
- Congenital Anomaly/Birth Defect
- Required Medical or Surgical Intervention to Prevent Permanent Impairment or Damage (Devices)
- Other Serious (Important Medical Events)

Please see instructions for block **B2** for further information on each of these criteria.

Product problem (e.g., defects/malfunctions): Any report regarding the quality, performance, or safety of any medication, medical device or special nutritional product. In addition, please select this category when reporting device malfunctions that could lead to a death or serious injury if the malfunction were to recur. Product problems include, but are not limited to, such concerns as:

- Suspected counterfeit product
- Suspected contamination
- Questionable stability
- Defective components
- Therapeutic failures (product didn't work)

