Disability or Permanent Damage: Check if the adverse event resulted in a substantial disruption of a person's ability to conduct normal life functions. Such would be the case if the adverse event resulted in a significant, persistent or permanent change, impairment, damage or disruption in the patient's body function/structure, physical activities and/or quality of life.

Congenital Anomaly/Birth Defect: Check if you suspect that exposure to a medical product prior to conception or during pregnancy may have resulted in an adverse outcome in the child.

Required Intervention to Prevent Permanent Impairment or Damage (Devices): Check if you believe that medical or surgical intervention was necessary to preclude permanent impairment of a body function, or prevent permanent damage to a body structure, either situation suspected to be due to the use of a medical product.

Other Serious (Important Medical Events): Check when the event does not fit the other outcomes, but the event may jeopardize the patient and may require medical or surgical intervention (treatment) to prevent one of the other outcomes. Examples include allergic bronchospasm (a serious problem with breathing) requiring treatment in an emergency room, serious blood dyscrasias (blood disorders) or seizures/convulsions that do not result in hospitalization. The development of drug dependence or drug abuse would also be examples of important medical events.

B3: Date of Event

Provide the actual or best estimate of the date of first onset of the adverse event. If day is unknown, month and year are acceptable. If day and month are unknown, year is acceptable.

- When a newborn baby is found to have a congenital anomaly, the event onset date is the date of birth of the child.
- When a fetus is aborted because of a congenital anomaly, or is miscarried, the event onset date is the date pregnancy is terminated.
- If information is available as to time during pregnancy when exposure occurred, indicate that information in narrative block **B5**.

B4: Date of this Report

The date the report is filled out.

B5: Describe Event, Problem or Product Use Error

For an **adverse event**:

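### Section 10.1.2 defines an SAE by unexpectedness and CTCAE grade with no patient-outcome criterion, although Section 10.1.1 relies on it to say when a hospitalization is serious

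*Combined protocol and SAP*

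**What the plan says.** Section 10.1.2 opens its definition with "A serious adverse event (SAE) is defined as" and then lists two qualifying conditions. One is that the event is unexpected, meaning not listed in Section 5.1. The other is "AE whose grade has increased to grade 3 or 4". Further down, the same section glosses SAEs as toxicities of Grade 3 or 4. It does not mention hospitalization, disability, threat to life or important medical events.

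Section 10.1.1 deals with hospitalization. Admissions that the disease makes expected, and those unrelated to drug or disease, are to be reported as ordinary adverse events "unless it meets the requirements for a serious adverse event (SAE) which can be found in Section 10.1.2". It adds that diagnostic, routine, planned-surgery and social admissions do not count as hospitalization in the serious sense. It also has its own grade rule: a rise to Grade 4 or 5 makes an event an SAE.

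The summary table in Section 10.1 requires no expedited report for expected events of Grades 1 to 3.

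Appendix F attaches a MedWatch form and its instructions. There, "An event is classified as serious when the patient outcome is" one of a list that includes death, threat to life, "Hospitalization - initial or prolonged", and disability or permanent damage.

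**The concern.** Seriousness describes what happened to the patient. Grade measures severity, and expectedness depends on a reference list. Section 10.1.2 uses the second and third in place of the first. An event on the expected list that stays below Grade 3 can therefore put a patient back in hospital without meeting any written SAE criterion.

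Section 10.1.1 shows that an outcome criterion was probably intended. Excluding certain admissions from the serious sense makes sense only if other admissions can be serious. The rule that would say so is missing from the section it points to.

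At stake is whether site staff classify the same readmission consistently, and whether it reaches the IRB, the FDA and the Medical Monitor by the expedited route. In the protocol's own words (Section 5.1) M032 has not yet been used in humans, so that route should not depend on individual interpretation.

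**Working it through.** No sample size, rate or test is involved. The check is to take specific events through each rule.

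**Case A: a single seizure after M032 that leads to readmission.**

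1. Is it unexpected? No. Seizure is on the Section 5.1 list and in Appendix A.
2. Is it Grade 3 or higher? The Section 4.2 table gives Grade 3 seizure as "Multiple seizures despite medical intervention". A single seizure falls short of that. I assume it has no feature that would grade it higher; the protocol does not reproduce the Grade 4 wording.
3. So neither listed condition in Section 10.1.2 is met, nor its Grade 3 or 4 gloss, nor the rise to Grade 4 or 5 in Section 10.1.1.
4. Does the readmission itself qualify? Section 10.1.1 refers this to Section 10.1.2, which has no such criterion. If the admission is drug-related, Section 10.1.1 does not even supply a default.
5. Does the summary table require an expedited report? No, because the event is expected and below Grade 4.
6. Under the Appendix F instructions the readmission makes it serious. They also give "seizures/convulsions that do not result in hospitalization" as an example of an important medical event.

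**Case B: an unexpected Grade 1 event with no consequence.** It meets the first condition in Section 10.1.2, so it is nominally an SAE, although the same list says Grade 1 needs no expedited report. Under Appendix F it is not serious.

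**Case C: expected limb weakness that becomes disabling.** The Section 4.2 table places disabling weakness at Grade 3, so the gloss in Section 10.1.2 makes it an SAE with notification within 24 hours. The summary table asks for no expedited report for an expected Grade 3 event.

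| Case | Section 10.1.2 | Summary table | Appendix F |
|---|---|---|---|
| A. Expected, below Grade 3, readmitted | No criterion met | No expedited report | Serious |
| B. Unexpected, Grade 1, no consequence | Nominally an SAE | No expedited report | Not serious |
| C. Expected, Grade 3, disabling | SAE, 24-hour notice | No expedited report | Serious |

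Case A shows the gap, case B shows the definition reaching too far, and case C shows the grade statements disagreeing with one another.

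**How wide the gap could be.** Section 5.1 lists 9 × 3 = 27 terms plus 8 more, 35 in all. Death cannot be low grade, so at most 35 − 1 = 34 terms could fall in the gap. Only seizure can be demonstrated from the documents. For most other terms it depends on CTCAE v4.0 wording that the protocol does not reproduce.

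**The case against.** The strongest reply is that little is lost, and most of it stands.

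- **Recording and review continue.** Section 10.1.1 puts every adverse event up to 30 days after dosing on the CRF whatever its relationship to drug. The Section 8 calendar schedules adverse event evaluation through Month 12. Section 10.2 has the DSMB reviewing all adverse events, quarterly and in real time. Section 11.1 tabulates all events. The DLT definition (Section 4.2) and halting rules (Section 4.5) do not use SAE status. A reader might infer that the DSMB would not see these events or that the safety conclusion would omit them. The documents do not support that.
- **The text is ambiguous, not categorical.** A reader might infer that an expected low-grade event that readmits a patient can never be an SAE. Section 10.1.1 implies that some admissions are serious, so an investigator could reasonably classify one that way. What is missing is a written criterion.
- **Disability is mostly covered by grade.** A reader might extend the point to disabling events. The Section 4.2 table already makes disabling gait disturbance and limb weakness Grade 3, so that extension largely fails.
- **Appendix F is not a rival trial definition.** The attached form is the voluntary FDA 3500, while the appendix text names 3500A. Its instructions say that investigational-drug events follow the study protocol. Section 10.1 therefore governs. That limits the form's weight as evidence of conflict, but it also means the form cannot supply the missing criterion.

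What survives is that the governing section has no outcome criterion and a cross-reference relies on one being there.

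**Conclusion.** The point holds in a limited form. Section 10.1.2 defines seriousness without any patient outcome, and the hospitalization rule in Section 10.1.1 points to a criterion that does not exist. Followed literally, an expected event below Grade 3 that causes readmission is neither classified as an SAE nor reported on an expedited basis. The consequence is confined to SAE classification and expedited reporting. Dose finding, the primary endpoint, adverse event recording and DSMB review are unaffected.

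The size cannot be put in patients, because the documents give no readmission rate for expected low-grade events. The conclusion rests on the text alone and on the assumption that the single seizure in the example is graded below 3. It is a fault in a stated rule, worth correcting because safety is the primary objective and the correction is a matter of wording.

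**What to change.** In Section 10.1.2, state one outcome-based definition. An SAE is an adverse event of any grade, expected or not, that results in death, is life-threatening, requires initial or prolonged hospitalization, causes disability or permanent damage, is a congenital anomaly, or is otherwise an important medical event. Keep the admission exclusions in Section 10.1.1, and state that the planned Day 0 to Day 3 stay is not itself an SAE.

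Use grade, expectedness and attribution only to set reporting timelines. Then bring four places into line, or grade-based definitions will remain:

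- the rise to Grade 4 or 5 in Section 10.1.1;
- the unexpectedness and Grade 3 or 4 conditions in Section 10.1.2;
- the gloss in Section 10.1.2 that equates SAEs with Grade 3 or 4 toxicities;
- the summary table's exemption of expected Grades 1 to 3.

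The mismatch between the form named in Appendix F and the one attached can be corrected in the same amendment.

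The cost is an edit to Section 10.1 and a few more SAE forms. No visit, procedure or staff is added.
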